11.5 Pharmacokinetic assessments

11.5.1 Blood sampling for analysis of systemic concentration of delgocitinib

A single blood sample for PK assessment will be collected for each subject after 2–6 hours after the morning application of IMP as specified in the schedule of trial procedures (Section 4). The PK blood sample should be collected from a non-treated area.

It will be recorded in the eCRF if the PK blood sample was taken; if not, a reason will be provided. The date and time of the last IMP application prior to the PK sample being taken must be recorded in the eCRF.

Collection, handling and shipment instructions for PK blood samples are provided in a laboratory manual.

Plasma samples for determination of delgocitinib concentration will be analysed by a laboratory using a validated bioanalytical method. Details of the analytical method used will be described in the bioanalytical report.

Samples from delgocitinib cream vehicle-treated subjects will not be analysed. Written procedures are in place to avoid unblinding of the trial and any trial subjects in relation to analysis of the PK samples.

11.6 Pharmacodynamics and pharmacogenomics

11.6.1 Overview

Normal skin is colonised by a wide variety of microorganisms, including fungi, viruses, and bacteria. The skin microbiome is complex and diverse and varies between individuals and anatomical sites (Costello et al. 2009). It has been known for years that some skin diseases are associated with dysbiosis of the skinbiome. AD has long been associated with increased skin colonisation with *S. aureus*. Indeed, *S. aureus* colonisation has been proposed to play an important role in AD pathophysiology via bacterial production of specific virulence factors (Cardona et al. 2006). Increased colonisation with *S. aureus* in AD is accompanied by decreased colonisation with many commensal bacterial species, resulting in overall decrease in bacterial diversity (Kong et al. 2012). Resolution of active-disease in AD in response to therapy correlates with reduction of *S. aureus* colonisation and increase in microbiome diversity (Kong et al. 2012).

The present trial will use sequencing to identify specific strains of bacteria present on the skin and thus characterise treatment effects on the skin microbiome in AD subjects.

A summary of the results will be included in the CTR if they are available in time for this. The full pharmacodynamics/biomarker results will be reported in an addendum report to the CTR.

11.6.2 Skin swabs

A total of 4 skin swabs for microbiome and *S. aureus* measurements will be taken at the time points specified in the schedule of trial procedures (Section 4).

At baseline (Day 1), 2 skin swabs are to be taken:

- 1 skin swab from a representative lesional area. The location should be selected so that a similar non-lesional body location can be identified.
- 1 skin swab from a non-lesional area at an anatomically similar site to the lesional skin swab.

At Week 8 (end of treatment), 2 skin swabs will be taken at the same locations as the baseline skin swabs.

If biopsies are to be taken (see Section 11.6.3), the baseline biopsies will be taken from the same area as the skin swabs, so the sites selected for skin swabs must then also be appropriate for biopsying.

It will be recorded in the eCRF if the skin swabs were taken and from which location (volar arm, lower limbs, trunk, other); if skin swabs were not taken, a comment will be provided.

Subjects will be instructed not to shower or wash their body for at least 10 hours prior to the baseline visit and Week 8 visit.

Further instructions for collection, handling and shipment for skin swabs are provided in a laboratory manual.

11.6.3 Skin biopsies and photographs (all sites, but optional)

Subjects who have lesions at a location suitable for biopsying (i.e. volar arm, lower limbs, trunk, other) will be asked to participate in an exploratory component involving skin biopsies. Participation in this component of the trial requires that the subject provides additional informed consent and is not mandatory for participation in the trial. Biopsies will not be taken if the investigator considers the procedure unsuitable for the subject (e.g. subjects receiving anticoagulant therapy).

It is expected that approximately half of the eligible subjects will accept to participate in this exploratory component of the trial. If biopsies are obtained from less than 10% of subjects, analysis may not be carried out as the number of biopsies may be too low to allow for a meaningful analysis. A final decision will be made after unblinding.

The skin biopsies will be used to analyse the expression of genes involved in the pathogenesis of AD including inflammatory genes, genes involved in immune function and genes involved in skin differentiation and barrier function. If deemed relevant transcriptome profiling of some or all of the biopsies may be done. The purpose is to assess if changes in gene expression precedes the clinical effect of JAK inhibition and to show disease resolution also at the molecular level.

A total of four skin biopsies (2 mm) will be taken at the timepoints specified in the schedule of trial procedures (Section 4): at baseline (lesional and non-lesional skin), after 1 week of treatment (lesional only) and at end of treatment (lesional only).

Skin biopsies will be taken from the same body location as the skin swabs. It will be recorded in the eCRF if the biopsy was taken and from which body location (volar arm, lower limbs, trunk, other); if not, a comment should be provided. All four biopsies will be from an anatomically similar body location to the extent possible.

A check of skin biopsy wound healing including removal of suture, if applicable, will be performed at the next trial visit as specified in the schedule of trial procedures (Section 4).

The biopsies will be transferred to RNAlater (RNA stabilisation) solution immediately after being collected and placed at 2–8°C for 16–30 hours. The sample will then be transferred to a clean tube and stored at <-20°C in suitable rack and kept until shipment to the central laboratory for further processing. Further instructions for collection, handling, and shipment for skin biopsy samples are provided in a laboratory manual.

It is recommended to document the biopsied areas with photographs taken before biopsying and immediately after, both at baseline, after 1 week of treatment and at the end of treatment, using digital photography assessments. This will serve both as a documentation of the biopsy site and to show disease progression over time. The photography component for the skin biopsies is recommended and not mandatory.

The trial sites participating in this photography component will be expected to use their own equipment to take the photographs. Instructions and specifications for photography will be provided in a photography manual.

The photographs will have no other subject identifier than the subject ID and visit number and will be transmitted electronically using a secure file transfer protocol. Features that could potentially be used to identify the subject e.g. tattoos or jewelry will be removed from the photographs before they are transferred to LEO.

Printed copies of the photographs must be included as part of the individual subject source documentation.

LEO may at its discretion use the photographs in publications, posters, and similar types of information material or media targeting patients and health care professionals. The photographs may also be part of training material used for training and educational purposes. Steps will be taken to ensure that the identity of the subject is protected to the extent possible.

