14.2 Trial analysis sets

All screened subjects will be accounted for in the CTR.

All randomised subjects exposed to IMP will be included in the full analysis set and will be analysed for efficacy parameters up to Week 8. Exclusions from the full analysis set can be considered in special cases as described in ICH E9, Section 5.2.1, Full Analysis Set. If it is decided to exclude a subject from the full analysis set, a justification addressing ICH E9 will be given.

A per protocol analysis set will be defined by excluding subjects from the full analysis set who fulfil any of the following criteria:

- Did not provide EASI or vIGA-AD data following start of treatment.
- Are known to have taken the wrong IMP throughout the treatment period of the trial.
- Did not fulfil the disease defining inclusion criteria (that is, inclusion criteria 3, 4, 5, and 6).
- Did not apply IMP at least 80% of the time in the period from date of first application of IMP to date of last application of IMP.

A safety analysis set will be defined as all randomised subjects exposed to IMP.

The decisions regarding inclusion/exclusion of subjects and/or subject data from the trial analysis sets will be documented in the analysis set definition document before breaking the randomisation code.

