14.3.12 General principles

Unless otherwise stated, all significance tests will be 2-sided using the 5% significance level. All CIs will be presented with 95% degree of confidence.

An observed-cases approach will be used for tabulations of data by visit (i.e. involving only those subjects who attended each specific visit).

Categorical data will be summarised using the number and percentage of subjects in each category and treatment group. Continuous data will be summarised using the mean, median, standard deviation, minimum, and maximum values.

All the analyses specified in the protocol will be reviewed in relation to the blinded data actually obtained and the statistical analysis plan will be finalised before breaking the randomisation code.

Any changes from the statistical analysis planned in this clinical trial protocol will be described and justified in a protocol amendment, the statistical analysis plan and/or in the CTR dependent on the type of deviation.

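### If few subjects give skin biopsies, whether to analyse them is decided after unblinding, although the deciding count is available while the trial is still blinded

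*Combined protocol and SAP*

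**What the plan says.** Section 11.6.3 describes the biopsies as an optional, exploratory component with separate consent. On uptake it says: "It is expected that approximately half of the eligible subjects will accept to participate". On low uptake it says: "If biopsies are obtained from less than 10% of subjects, analysis may not be carried out", the reason being that the number might be too small to be informative. The next sentence is "A final decision will be made after unblinding". The section states no per-arm criterion and does not say why treatment codes are needed.

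The same section provides the record from which the criterion can be counted: "It will be recorded in the eCRF if the biopsy was taken and from which body location". Appendix 3D adds that the sponsor can see eCRF entries as soon as they are made, and that entry is due within 5 working days of each visit unless the site contract says otherwise.

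Two passages in Section 14 show how the plan handles comparable choices. Section 14.3.12 has the planned analyses reviewed on blinded data, and "the statistical analysis plan will be finalised before breaking the randomisation code". Section 14.2 has decisions on which subjects and data enter the analysis sets "documented in the analysis set definition document before breaking the randomisation code".

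Panel 3 (Section 6) lists two endpoints that depend on the biopsies, under other endpoints: change in gene expression from baseline to Week 1 and to Week 8. Section 14.3.8 calls the biomarker analyses exploratory and sends the full results to an addendum to the clinical trial report.

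**The concern.** A feasibility rule that depends only on how many subjects gave a biopsy needs no knowledge of who received what. Placing the decision after unblinding lets it be taken when efficacy by arm may already be visible. The rule is also permissive: below 10% the analysis may be dropped but need not be, so the count alone does not settle the matter and judgement remains.

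At stake is how far two listed endpoints can be trusted if uptake is low. Section 11.6.3 says the biopsies are meant partly to show that the disease resolves at the molecular level as well. If their analysis is run or dropped after the clinical result is known, a feasibility decision is harder to tell from one influenced by the results, particularly if the number biopsied is not reported alongside it.

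**Working it through.** The plan gives no calculation behind the 10% threshold, so there is none to reproduce. The sample-size calculation in Section 14.1 concerns EASI and is not involved. The check is mainly one of timing, with simple arithmetic for size.

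**1. When the deciding number is known.** The input is the share of subjects with biopsies. Biopsies are scheduled at Day 1, Week 1 and Week 8 (Panel 2), and each is recorded in the eCRF. The overall count is therefore complete, without codes, at the latest once the last Week 8 visit has been entered. Nothing in the criterion changes at code break.

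**2. How this sits beside the plan's other rules.**
- Analysis-set decisions (14.2): before code break.
- Statistical analysis plan (14.3.12): final before code break, after blinded review.
- Decision on biopsy analysis (11.6.3): after unblinding.

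The third is out of line with the first two.

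**3. The size of the threshold.** Inputs: 250 randomised subjects in five equal groups (14.1) and the 10% rule (11.6.3). The text does not name the denominator; randomised subjects are assumed.
- Threshold: 0.10 × 250 = 25 subjects, so the low-uptake case is 24 or fewer.
- Average per arm at the threshold: 25 / 5 = 5.
- Expected number if all 250 are eligible for biopsy: 0.50 × 250 = 125, or 125 / 5 = 25 per arm.

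**4. How likely the low-uptake case is.** Let X be the number biopsied, X ~ Binomial(250, p). Here p is overall uptake, that is, the acceptance rate times the share of subjects eligible for biopsy. The plan gives acceptance of about 50% but no eligible share, so p is varied. The middle column is p / 0.50.

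| Overall uptake p | Eligible share implied at 50% acceptance | P(X ≤ 24) |
|---|---|---|
| 50% | 100% | about 10⁻⁴² |
| 30% | 60% | about 7 × 10⁻¹⁵ |
| 20% | 40% | about 0.0007% |
| 15% | 30% | 0.8% |
| 12% | 24% | 14% |
| 10% | 20% | 47% |
| 8% | 16% | 85% |

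Only the 50% acceptance rate comes from the plan; every other uptake is an assumption. The binomial model treats subjects as independent. If whole sites took no biopsies, the count would vary more than shown. On the plan's own expectation the case is remote. It becomes a practical possibility only if overall uptake falls to roughly 12% or less.

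**5. What is exposed if it happens.** The two gene-expression endpoints in Panel 3. The primary endpoint and the three secondary endpoints are clinical assessments (EASI and vIGA-AD) and do not use the biopsies.

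**The case against.** The best argument for waiting is that, with five arms, whether an analysis is informative depends on how the biopsies fall across arms. Randomisation is stratified by severity and region, not by biopsy consent, so the actual spread is hidden until code break. The variation is real: if 25 biopsied subjects fall at random over five equal arms, the smallest arm has 2 or fewer in about 45% of simulated allocations, and 1 or none in about 14%. What stands is that the sponsor loses something by deciding blind. What does not stand is the argument as a defence of the text, because the plan states an overall percentage and no per-arm criterion.

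Three stronger readings are tempting and are not supported.

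- *The biopsies can be dropped at any uptake.* The sentence on timing directly follows the 10% clause and most naturally belongs to it, although it is not expressly limited to that case. Above the threshold no option to drop is stated: Section 11.6.3 commits the biopsies to gene-expression analysis, and Section 14.3.8 says biomarker analyses will be performed.
- *Section 11.6.3 contradicts Section 14.3.12.* A final statistical analysis plan could contain a later decision point, and Section 14.3.12 itself allows changes to be described and justified in the clinical trial report. Nor does the plan close every choice in advance. On the assay it says: "If deemed relevant transcriptome profiling of some or all of the biopsies may be done", with no timing given. This is a departure from general practice, not a contradiction.
- *A reader could never detect a results-driven omission.* The endpoints, the threshold and the addendum are all stated in advance, so an omission could be set against the number biopsied, provided that number is reported.

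**Conclusion.** The point holds in a limited form. Section 11.6.3 puts after unblinding a decision whose only stated criterion can be counted while blinded, gives no reason, and so departs from the practice in Sections 14.2 and 14.3.12. The exposure is confined to the case of fewer than 10% of subjects, about 25 of 250, which is very unlikely at the expected uptake. It touches two exploratory endpoints. It would be wrong to infer any effect on the dose-response conclusion, the secondary endpoints, sample size or power. It would be equally wrong to infer an intention to report selectively: the text leaves the route open and says no more.

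This rests on three assumptions: that the 10% refers to randomised subjects, that the timing sentence applies to the low-uptake case, and that no separate statistical analysis plan already sets an earlier decision. If one does, only Section 11.6.3 needs aligning. The point is a worthwhile small improvement, not a serious flaw.

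**What to change.** Replace the sentence on timing in Section 11.6.3 with:

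*The decision will be made on the blinded overall count of randomised subjects with biopsies obtained, as recorded in the eCRF, and documented in the statistical analysis plan before the randomisation code is broken; the number of subjects biopsied and the decision will be reported in the CTR.*

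This names the denominator and uses a count the eCRF already holds, so it does not wait on laboratory processing or need anyone unblinded. The sponsor keeps its discretion below 10% but exercises it without treatment codes, and the reporting clause lets a reader check the decision against the number biopsied.

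The cost is one sentence. Trial procedures, sample size and power do not change. The one thing given up is the option of seeing how the biopsies are spread across arms before deciding.

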11.7 Other assessments

11.7.1 Patient-reported outcomes (PROs)

Each subject must make individual assessments relating to their perception of their disease and quality of life. These will be performed prior to the investigator performing his/her efficacy assessments. At the screening visit, the subject's eligibility needs to be established before the PROs can be completed.

The subjects will receive an eDiary device and eDiary training, as well as complete all of the PROs (except TSQM), at the screening visit. Completion of the eDiary will be initiated at the latest 1 week prior to the baseline visit (Day 1).

Two PROs will be assessed daily using an eDiary:

- ADSD.
- Eczema-related Sleep NRS.

The subjects must complete the eDiary each day in the evening, and compliance with the eDiary completion will be reviewed by the trial site staff throughout the trial. The eDiary should be returned to the trial site as outlined in the schedule of trial procedures (Section 4).

In addition, 8 PROs will be completed on an electronic device by the subjects at the trial sites at the visits specified in the schedule of trial procedures (Section 4). The PROs will be completed in the following order:

- POEM.

- DLQI.
- PGI-S.
- PGI-C.
- SF-36.
- EQ-5D-5L.
- WLQ.
- TSQM.

11.7.1.1 Atopic Dermatitis Symptom Diary (ADSD)

ADSD is a symptom diary developed by LEO. CCI

CCI

CCI

CCI

CCI

11.7.1.2 Eczema-related Sleep Numeric Rating Scale (Eczema-related Sleep NRS)

Eczema-related Sleep NRS is a scale developed by LEO. Subjects will rate how much their eczema interfered with their sleep the previous night using an 11-point NRS (0 indicating it 'did not interfere' and 10 indicating that it 'completely interfered'). Subjects will complete the Eczema-related Sleep NRS as part of an eDiary each day in the evening at the latest from Week -1 to Week 8.

11.7.1.3 Patient-Oriented Eczema Measure (POEM)

POEM is a validated questionnaire used to assess disease symptoms in AD patients in both clinical practice and clinical trials ([Charman et al. 2004](#)).

The tool consists of 7 items each addressing a specific symptom (itching, sleep, bleeding, weeping, cracking, flaking, and dryness). Subjects will score how often they have experienced each symptom over the previous week on a 5-point categorical response scale (0 = 'no days'; 1 = '1 to 2 days'; 2 = '3 to 4 days'; 3 = '5 to 6' days; 4 = 'every day'). The total score is the sum of the 7 items (range 0 to 28) and reflects disease-related morbidity; a high score is

indicative of a worse disease severity. The POEM will be completed at the trial site according to the schedule of trial procedures ([Panel 2](#)).

11.7.1.4 Dermatology Life Quality Index (DLQI)

DLQI is a validated questionnaire with content specific to those with dermatology conditions. It consists of 10 items addressing the subject's perception of the impact of their skin disease on different aspects of their quality of life over the last week. These include dermatology-related symptoms and feelings, daily activities, leisure, work or school, personal relationships and the treatment ([Finlay & Khan 1994](#)). Each item is scored on a 4-point Likert scale (0='not at all/not relevant'; 1='a little'; 2='a lot'; 3='very much'). The total score is the sum of the 10 items (0 to 30); a high score is indicative of a poor quality of life. The DLQI will be completed at the trial site according to the schedule of trial procedures in [Section 4](#).

11.7.1.5 Patient Global Impression of Severity (PGI-S)

PGI-S is a single item designed to capture the subject's overall perception of their eczema over the past week on a 4-point categorical response scale ('none' to 'severe'). The PGI-S will be completed at the trial site according to the schedule of trial procedures ([Section 4](#)).

11.7.1.6 Patient Global Impression of Change (PGI-C)

The PGI-C is a 1-item questionnaire designed to assess the subject's overall impression of changes ([FDA public workshop on Guidance 3 2018](#)). The subjects have to select the one response from the response options ('much better', 'a little better', 'no change', 'a little worse', or 'much worse') that best describes the overall change in their eczema since they started IMP treatment. The PGI-C will be completed at the trial site according to the schedule of trial procedures in [Section 4](#).

11.7.1.7 36-item Short Form Health Survey (SF-36)

The SF-36v2 (Acute Recall) is a 36-item scale constructed to survey health status and quality of life ([Ware & Sherbourne 1992](#)). The acute recall version asks subjects to reply to questions according to how they have felt over the previous week. Subjects will be asked to answer each item by selecting one of 3 to 6 categorical response options.

The SF-36v2 (Acute Recall) yields scores for 8 health domains (physical functioning, role physical, bodily pain, general health, vitality, social functioning, role emotional, and mental health) and 2 psychometrically derived summary scores (a physical component summary and a mental component summary).

The SF-36 will be completed according to the schedule of trial procedures in Section 4.

